- Renal function tests: Serum creatinine, BUN, sodium, potassium, chloride, and eGFR. Serology tests: human immunodeficiency virus, hepatitis B virus, and hepatitis C virus tests (only at Visit 1)
- At Visit 1, 7 and 8
 - Urine samples were collected for: Urine pregnancy test (UPT): Only for females of childbearing potential or who are ≤ 1 year postmenopausal prior to enrolment
- At Visits, 1, 3, 4, and 6:
 - Fasting plasma glucose level (also prior to dosing at Visit DE 1 and DE 2);
 - 2-hour PPG level (also prior to dosing at Visit DE 1 and DE 2)
- At Visit 1 only:
 - Haematology: RBCs count, Hb, platelet count, WBCs count including differential count (only at Visit 1)
 - Serology tests: human immunodeficiency virus (HIV), hepatitis B virus (HBV), and hepatitis C virus (HCV) tests
 - Urinalysis: routine examination (also at Visit 8)
 - Urine samples were collected for the following tests
 - At Visit 1, 7, and 8: Urine pregnancy test (UPT): Only for females of childbearing potential or who are ≤ 1 year postmenopausal prior to enrolment
 - At Visit 1 only: Urinalysis: routine examination

Any additional laboratory tests if required during the study period could be done at local accredited laboratory.

Immunogenicity Assessment: Insulin Antibody test - Anti-insulin antibody (AIA)

The immunogenicity of the IP was assessed using validated assays. Blood samples (1 x 3.5 mL) were collected at screening visit (Visit 1), End of treatment visit (Visit 7) and Post treatment follow-up visit (Visit 8) for testing presence of anti-insulin antibodies to the IP. The procedure for sample handling, storage and analysis was provided in the central laboratory manual.

Emergency Contact

In case of any emergency, the site contacted the medical monitor from the CRO. The medical monitor provided guidance in case of any emergency related to safety of the subject.

Other Study Assessment

Body Weight, Waist circumference and Body mass index

Body weight was measured at every study visit in kg. Body mass index (BMI) (kg/m^2) and waist circumference (cm) was calculated at all study visits, except Visit DE 1 and Visit DE 2.

Body mass index (BMI) was calculated by formula:

$$BMI = \frac{Weight \ (kg)}{height^2 \ (m)^2}$$

Appropriateness of Measurements

All clinical measurements were performed using standard methods that were generally recognized as being reliable, accurate, and relevant.

Primary Variable(s):

Efficacy Assessment:

- Glycated haemoglobin (HbA1c)

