- Fasting plasma glucose (FPG)
- 2-hour post prandial plasma glucose (2-hour PPG)

Safety Assessments:

- AEs and SAEs (serious and non-serious AEs) were collected for relatedness, severity, seriousness, and outcome, including events of hypoglycaemia were collected once the signed informed consent was obtained from the subject
- Vital signs: Pulse rate (PR), respiratory rate (RR), systolic blood pressure (BP) and diastolic BP (in supine position after 5 minutes of rest), and body temperature (at all visits)
- Physical examination 12-Lead electrocardiogram (ECG)
- Laboratory investigations:
 - Lipid profile: Total cholesterol, high density lipoprotein (HDL), low density lipoprotein (LDL) very low-density lipoprotein (VLDL) and triglycerides after at least 12 hours of fasting
 - o Liver function tests: ALT, AST, and total bilirubin
 - Renal function tests: serum creatinine, eGFR, sodium, potassium, chloride, and BUN
 - Urine pregnancy test (UPT): Only for female subjects who are of childbearing potential or who are ≤ 1 year postmenopausal prior to enrolment in the study.

The Investigator described severity, relatedness, and outcome of every AE. The severity of the AE was graded according to NCI-CTCAE version 4.0 on a five- point scale (Grade 1 to Grade 5).

https://evs.nci.nih.gov/ftp1/CTCAE/CTCAE_4.03/Archive/CTCAE_4.0_2009-05-29 QuickReference 8.5x11.pdf

Secondary variable(s):

Immunogenicity Assessments

• Insulin Antibody test: Anti-insulin antibody (AIA)

Pharmacovigilance-Relevant Information

Not Applicable.

Data Quality Assurance

Audits and Inspections

Not applicable.

Data Handling

The Investigator maintained all documentation relating to this study. Essential documents (as defined in the ICH-GCP) are retained until at least 2-years after the last approval of a marketing application in an ICH region, and until there were no pending or contemplated marketing applications in an ICH region or at least 2-years have elapsed since the formal discontinuation of clinical development of the IP. These documents must be retained for a longer period, however, if required by the applicable regulatory requirement(s) or if needed by sponsor.

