Prior and concomitant medications were coded using the standard WHODD dictionary prior to analysis. Counts and percentages were presented by drug class and generic term for descriptive summarization.

Efficacy Analyses

Primary Analysis

The primary endpoint was change in HbA1c level post 12-week administration of selected fixed dose of USVCAP (75 IU, or 150 IU or 300 IU) from baseline visit within each treatment group. The actual measurement of efficacy endpoint was summarized using number of subjects (n), mean, SD, median, and minimum and maximum (range) and 95% confidence interval (95% CI) for each treatment group at both baseline and EOT (End of treatment) visits along with change from baseline to EOT for each treatment group.

The statistical analysis for the primary endpoint were carried out to compare the change in HbA1c post 12-week administration of selected dose of USVCAP from baseline visit within each of the 3 dosing groups by using paired t-test.

In addition to evaluate primary efficacy within each randomly assigned groups as planned, we also evaluated a subgroup analysis on those patients who had uncontrolled hyperglycaemia and those who had not to see the robustness of the data on primary efficacy parameter.

Secondary Analysis

The secondary endpoint of comparing the change in HbA1c post 12-week administration of USVCAP from baseline between the 3-fixed dose groups to examine the dose response relationship between them; analysis of covariance (ANCOVA) with dose groups (treatment groups), visit and interaction between visit and treatment as factors and baseline HbA1c value as covariates using Proc mixed was used. ANCOVA model determined the statistically significant difference between different dose groups on change in HbA1c from baseline to 12-week treatment with USVCAP, controlling for the effect of the baseline HbA1c value as covariate. Also, applying same ANCOVA model and coefficient estimate for dose factor, further pairwise comparisons of the three experimental dose levels for change in HbA1c post 12-week treatment with USVCAP examined the dose response relationship.

Similarly, ANCOVA model were also applied to analyze the change in fasting and postprandial plasma glucose in each treatment group.

Details of the analysis were provided in statistical analysis plan.

Safety Analysis

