Summary tables were provided for prior/concomitant medications in the study.

Immunogenicity analyses

Partial correlation was used to measure the relationship between the percent change in HbA1c and percent change in anti-insulin antibodies with absolute change in total insulin dose as covariate from baseline to Visit 7 and Visit 8. Change in level of serum anti-insulin antibodies from baseline to Visit 7 and Visit 8 were compared through paired t-test within each treatment arms.

Statistical Significance

The level of significance in the primary analysis were set to 5%. The analyses was performed upon completion of the main trial period. All secondary analyses were also be performed at the 5% significance level.

Replacement of Subjects

The subject who discontinued from trial/withdrawn from the study treatment were not replaced.

Withdrawn Subject Data Collection

The subject could withdraw their consent from the trial, or this could be the Investigator's decision to discontinue the subject from trial; if they decided to do so, at any time and irrespective of the reason all efforts should be made to document the reason for treatment withdrawal/discontinuation from the trial (see section 11.5.1) and this should be documented in the e-CRF.

The Investigator/designee involved in the study documented the reason for the subject withdrawal as follows:

Subject's voluntary withdrawal of consent

Subject's non-compliance to the IP: Repeated missing of study medication doses

Protocol violation: Repeated non-follow-up for safety or efficacy procedures required for the study. Protocol violation may be also considered when the subject is not included as per protocol-defined eligibility criteria.

Any AE or SAE requiring subject withdrawal in the opinion of the Investigator: An AE form must be completed. Clinically significant abnormal value not explained by a laboratory error or being not a known or abnormal value commonly observed in this type of population was also considered as an AE or SAE, and recorded on AE form as applicable.

Requirement of prohibited medication: Recording of the details of prohibited medication were completed on the concomitant medication CRF page and the subject were withdrawn from the study.

Requirement of dose reduction for both IP and non-IP: If there was requirement for change in dose of the IP (which is not mentioned in the protocol) or non-IP at any point of time during the study period, the subject were withdrawn from the study.

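### HbA1c change is tested separately at three doses with no error control across doses (5% in one section, 2.5% in another), and the primary variable list does not match the primary endpoint

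*Combined protocol and SAP*

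**What the plan says.** All references are to the combined protocol and SAP.

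- **Variable lists.** Under the heading "Primary Variable(s", the efficacy items are HbA1c, "Fasting plasma glucose (FPG" and "2-hour post prandial plasma glucose (2-hour PPG", without ranking. Safety measurements follow under the same heading. The only entry under Secondary variable(s) is "Insulin Antibody test: Anti-insulin antibody (AIA".
- **Primary Analysis.** "The primary endpoint was change in HbA1c level post 12-week administration of selected fixed dose of USVCAP", measured from baseline within each group. The test is run "from baseline visit within each of the 3 dosing groups by using paired t-test".
- **Secondary Analysis.** After the between-dose comparison of HbA1c comes: "Similarly, ANCOVA model were also applied to analyze the change in fasting and postprandial plasma glucose in each treatment group".
- **Statistical Significance.** "The level of significance in the primary analysis were set to 5" per cent. Secondary analyses are also at 5%. No adjustment, testing order or rule on how many doses must succeed appears.
- **Determination of Sample Size.** Each dose group is sized on HbA1c alone, by a paired t-test at 2.5%, two-sided, with 90% power, giving 52 evaluable subjects per group.

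**The concern.** Two things do not fit together. FPG and 2-hour PPG are primary in the list of variables and secondary in the analysis text, so the document does not give one consistent statement of what the primary efficacy variable is.

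The larger issue is the error rate. The primary objective is to find a safe and effective dose among three doses of one product. Each dose has its own primary test, and nothing limits the chance that one of the three is significant by accident. The two significance levels in the text disagree, so a reader cannot tell which applies. At stake is whether a significant HbA1c result at a single dose carries the 5% error that the plan attaches to its primary analysis.

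**Working it through.** **Inputs.** From Determination of Sample Size: HbA1c 7.5 to 7.0 (difference 0.5), SD 1.0 before and after, effect size 0.5, alpha 2.5% two-sided, power 90%, drop-out 20%. From Statistical Significance: 5%. From Overview of Study Design: 153 randomised 1:1:1, so 153/3 = 51 per group. Derived, not stated: an effect size of 0.5 requires an SD of the difference of 1.0. Since that SD is √(1 + 1 − 2r), the pre-post correlation r must be 0.5.

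**Reproducing the plan's figure.** Normal approximation at 2.5% two-sided: ((2.2414 + 1.2816)/0.5)² = 49.6. Adding z²/2 = 2.2414²/2 = 2.5 gives about 52. The exact noncentral t calculation gives 53, with power 89.9% at 52, so 52 is reproduced within rounding. Then 52/0.80 = 65 and 65 × 3 = 195. At 5% two-sided the same calculation gives 44. The sample size therefore rests on 2.5% two-sided, not on the 5% in Statistical Significance.

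**Error over the three HbA1c tests.** The doses are separate groups of subjects, so the tests are independent. If no dose changes HbA1c:

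| Level per test (two-sided) | At least one significant | Counting only falls |
|---|---|---|
| 5% | 1 − 0.95³ = 14.3% | 1 − 0.975³ = 7.3% |
| 2.5% | 1 − 0.975³ = 7.3% | 1 − 0.9875³ = 3.7% |
| 1.67% (5%/3) | 1 − 0.9833³ = 4.9% | |

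A two-sided 5% corresponds to 2.5% in the direction of a fall. Both falls-only figures, 7.3% and 3.7%, exceed that.

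**Power under the planned effect of 0.5 SD** (exact noncentral t; Holm by simulation, three independent groups, all doses effective):

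| Analysed per group | 5% | 2.5% | 1.67% | Holm, mean per dose |
|---|---|---|---|---|
| 51 | 93.8% | 89.2% | 85.8% | 92.8% |
| 41 | 87.8% | 80.5% | 75.6% | 84.9% |

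The row for 41 is an assumption: 51 × 0.80 = 40.8, the plan's drop-out rate applied to the number randomised.

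**The case against.** **The variable list may only be an inventory.** It sits under Appropriateness of Measurements, includes vital signs, ECG and a pregnancy test, and gives no change, time point or test. The endpoint statement and the sample size both point to HbA1c alone. This stands: the mismatch is mainly one of labelling. A reader might infer nine primary tests (three variables by three doses) and an error of up to 1 − 0.95⁹ = 37.0%, or that the successful variable could be picked afterwards. The documents do not support that. They name HbA1c as the endpoint and give the paired t-test only to HbA1c; FPG and PPG get an ANCOVA under Secondary Analysis.

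**The 2.5% may have been meant to allow for several doses.** No passage says so, the analysis section says 5%, and 2.5% over three tests still gives 7.3%.

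**No success rule of at least one dose is written down.** True. Treating the three tests as one family is an inference from the primary objective. The text offers no alternative rule, however, and three separate tests at a flat level allow a claim from any one of them.

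**A separate, more detailed SAP is mentioned.** It may contain an adjustment. None appears in the text available, and the flat 5% and the 2.5% there would still disagree.

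**This is an open-label phase IIb study, reported in the past tense.** Formal control matters less than in a confirmatory trial, and a rule introduced now may be post hoc. That affects how it must be labelled, but not the arithmetic.

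**Conclusion.** The concern holds for the three HbA1c tests. With no true change at any dose, the chance of at least one significant result is 14.3% at 5% and 7.3% at 2.5%, so neither level holds the two-sided error over the doses at 5%. The conflict between 5% and 2.5% needs resolving in its own right. The different status of FPG and PPG in the two sections is a real inconsistency, but it does not justify an error rate built on nine tests.

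These rates rest on independent groups and on treating the three doses as one family. They concern only the null of zero pre-post change. The power figures also need the effect size of 0.5, which implies the unstated pre-post correlation of 0.5.

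**What to change.** 1. In the primary variable list, keep change in HbA1c at 12 weeks as the single primary efficacy variable and move FPG and 2-hour PPG to the secondary list, matching the analysis and sample-size sections.
2. In Statistical Significance and Determination of Sample Size, state one rule: the three within-dose HbA1c tests are controlled at an overall two-sided 5%, for example by Holm. Explain how the 2.5% used for sizing relates to that rule. A fixed sequence of doses would also do if the order was set in advance.
3. If results are already known, label the adjustment as post hoc, in line with the section on deviations from the statistical plan.

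**Cost.** These are wording changes and adjusted p-values; no new data are needed. With 51 analysed per group and all doses effective, Holm costs about 1 point of mean per-dose power against 5% (93.8% to 92.8%) and gains against the planned 2.5% (89.2%). If a dose must pass at 1.67%, as is close to the case when only one works, power is about 86%, a loss of 8 points against 5%. With 41 analysed, the figures are 87.8% to 84.9%, and 75.6% at 1.67%, a loss of about 12 points. A fixed sequence keeps 93.8% for the first dose at 51 per group, but the second depends on the first: 0.938² = 88.0% if both work.

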In any case, all study records are for at least 5 years after the completion or discontinuation of the study. The Investigator notified sponsor or its designee of any changes in the archival arrangements, including but not limited to archival at an off-site facility, transfer of ownership of the records in the event the Investigator left the site. Sponsor notified the Investigator in writing when the study-related records were no longer needed.

Statistical Methods Planned in the Protocol and Determination of Sample Size

The following is an outline of the statistical methodology that was used to report and analyse this study. A more detailed description is provided in a separate statistical analysis plan (SAP) that includes additional exploratory analysis not explicitly mentioned in the following sections.

Study Analyses Sets

The analyses was performed on the following trial populations.

- Randomized population: The randomized population consisted of all subjects who were randomized in the study
- Safety population: The safety population consisted of all subjects who were randomized and had received at least one dose of the IP.
- Full Analysis Population: The full analysis set population consists of all the subjects who are randomized into the study, received at least one dose of the IP from the assigned dose by randomization, and had at least one post baseline assessment.
- Per Protocol (PP) population: The per-protocol (PP) population was all the subjects in the FAS population who had completed the study and did not had any major protocol deviation.

Demographic and Other Baseline Characteristics

The demographic variables such as age, gender, ethnicity, body weight and height etc. and baseline status (medical history, physical exam, etc.) was summarized for both PP and full analysis populations.

The descriptive statistics for continuous variables were presented with number (n) of nonmissing observations, missing observations, Mean, Standard Deviation (SD), Median, Minimum and Maximum. For categorical data, descriptive statistics were presented with number of exposed subjects, and number (N) with percentage of observations in the various categories of the endpoint, where percentage were based on the exposed subjects.

Descriptive statistics were provided for body weight, waist circumference and BMI parameters. In addition, individual results were reviewed for any treatment-emergent changes of possible clinical significance.

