In this trial, safety analysis was used to perform the safety population (defined above). All safety endpoints were analysed based on descriptive statistics as described above for continuous and categorical variables and presented visit wise. The analysis of safety assessments in this study included summaries of the following categories of safety data collected for each subject.

- Adverse events (AEs)
- Physical examination
- Vital signs
- 12-lead ECG
- Laboratory investigations

Adverse Events

AEs and SAEs were coded by 20.1 version of MedDRA body system and preferred term and tabulated by indicating number and percentage of subjects and number of events. All the AEs were listed and categorized as TEAE and SAE before dosing and after dosing. All AEs, which occur after the first dose of the IP, were categorized as TEAEs i.e. AEs with onset date on or after the first dose of the IP. The TEAEs were tabulated and summarized for each treatment group as; overall TEAEs experienced by subjects during the study, TEAEs experienced by subjects during treatment with actual assigned dose of IP. All AEs were collected, evaluated and tabulated by system organ class (SOC), preferred term (PT), date of onset, relationship to the test drug, seriousness, severity, frequency, action taken, and outcome for each treatment group. Narratives of all SAEs

were presented. AE were compared between treatment groups by using Chi square/Fisher's exact test.

Vital Signs

Descriptive statistics were provided by treatment group for PR, RR, systolic and diastolic BP, and body temperature, etc. The vital signs were generated by visit as absolute values and the change from baseline were recorded. In addition, individual results were reviewed for any treatment-emergent changes of possible clinical significance.

Physical Examination

Descriptive statistics were provided by treatment group for each body system and the change from baseline were also recorded.

12-Lead Electrocardiogram

Descriptive statistics were provided. In addition, individual results were reviewed for any treatment-emergent changes of possible clinical significance.

Laboratory Assessments

Descriptive statistics were provided by treatment group for each clinical laboratory parameter and the change from baseline were also recorded. In addition, individual results were reviewed for any treatment-emergent changes of possible clinical significance.

Concomitant Medications

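### Read literally, the full analysis set drops run-in leavers from the 150 IU and 300 IU groups but keeps equally early 75 IU leavers who have a post-baseline assessment, so a dose comparison on that set depends on a post-randomisation event

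*Combined protocol and SAP*

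**What the plan says.** Under Study Analyses Sets, the FAS consists of randomised subjects who "received at least one dose of the IP from the assigned dose by randomization, and had at least one post baseline assessment". The safety set in the same list has no link to the assigned dose: "The safety population consisted of all subjects who were randomized and had received at least one dose of the IP". The per-protocol set is "all the subjects in the FAS population who had completed the study and did not had any major protocol deviation".

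The Overview of Study Design, Table 2 and the Investigational Product section give the timing:

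- Group A takes its assigned 75 IU twice daily from Day 1.
- Group B takes 75 IU for one week and starts its assigned 150 IU on Day 8.
- Group C takes 75 IU and then 150 IU for one week each, and starts its assigned 300 IU on Day 15.

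The run-in comes after randomisation in an open-label study. The dose is raised only if the investigator judges that the run-in was tolerated, and a subject who needs a dose change during run-in is withdrawn. Withdrawn subjects are called in for the end-of-treatment assessments.

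The primary analysis tests change in HbA1c "within each of the 3 dosing groups by using paired t-test". The secondary analysis compares the three doses by ANCOVA with baseline HbA1c as covariate, and a similar model is applied to fasting and postprandial glucose. Neither section names an analysis set. The Secondary Analysis section ends: "Details of the analysis were provided in statistical analysis plan". That SAP is not among the documents.

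**The concern.** Whether a leaver who has taken study drug enters the FAS depends on having reached the assigned dose. In Group A that happens with the first capsule. In Groups B and C it happens only after one or two weeks and an investigator's decision made with allocation known. Early leavers can therefore be removed from two groups and kept in the third.

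Those kept in Group A contribute an HbA1c taken within days of starting, or a screening value carried forward under the LOCF rule. Their counterparts in B and C contribute nothing. If the FAS as worded is used for the ANCOVA, the groups compared are no longer those created by randomisation, and part of any dose difference could come from who was excluded. The study's stated aim is to find a safe and effective dose, so this comparison matters although it is labelled secondary.

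**Working it through.** **The wording.** Two places favour the literal reading. The safety set asks for any dose of study drug, so the extra phrase in the FAS should mean something more. The Adverse Events section separates overall events from "TEAEs experienced by subjects during treatment with actual assigned dose of IP". Table 2 also labels the groups by assigned doses of 75, 150 and 300 IU.

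**The same calendar day in each group.** Day 8 is the first scheduled post-baseline visit for everyone: Visit 3 in Group A and DE 1 in Groups B and C. Consider a subject withdrawn that day after a week of 75 IU twice daily, with glucose, weight and vital signs recorded. In Group A both FAS conditions are met. In Group B or C, without escalation, the dose condition fails. By the planned days, the period in which a treated leaver is excluded on that condition alone is 0 days in A, 7 in B and 14 in C.

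**Inputs for size.** 153 randomised 1:1:1 gives 153/3 = 51 per group. The sample size table gives a change of 0.5, effect size 0.5, SD 1.0 before and after, and 20% dropout. As a check, d = 0.5, two-sided alpha 2.5% and 90% power give 49.6 by the normal approximation, 52.2 with the usual z²/2 correction and 53 by exact noncentral t (power 0.899 at 52). The plan's 52 is reproduced within rounding of method, and 52/0.8 = 65, 3 × 65 = 195. The SD of the change is therefore 0.5/0.5 = 1.0.

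**Standard error.** With SD 1.0 before, after and for the change, 1 = 1 + 1 − 2ρ, so ρ = 0.5. The unadjusted pairwise standard error is √(2/51) = 0.198. Adjusting for baseline multiplies it by √(1 − 0.5²) = 0.866, giving 0.171.

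**Run-in exits (assumed: 20% dropout spread evenly).**

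- Two weeks: 0.20 × 2/14 = 2.86% (linear) to 1 − 0.8^(2/12) = 3.65% (constant hazard), or 1.5 to 1.9 of 51.
- One week: 0.20/14 = 1.43% to 1 − 0.8^(1/12) = 1.84%, or 0.7 to 0.9 of 51.

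**Bias with no true dose effect.** Let continuers change by −0.5, exits by 0, with exits' baseline HbA1c like the rest and all early Group A exits kept.

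- C mean = −0.500, since its run-in exits are dropped.
- A mean = −0.5 × (1 − 0.0286) to −0.5 × (1 − 0.0365) = −0.486 to −0.482.
- A − C = 0.014 to 0.018. Divided by 0.171 this is 0.08 to 0.11 standard errors.
- B drops week-1 exits only, so A − B and B − C are each about 0.007 to 0.009.
- Two-sided error at a shift of 0.11: Φ(−2.07) + Φ(−1.85) = about 5.1% instead of 5.0%.

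**Sensitivity of A − C.**

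| Assumption | A − C (HbA1c points) |
|---|---|
| Half of early Group A exits have an assessment, zero change | 0.007 to 0.009 |
| All kept, exits change by +0.5 | 0.029 to 0.037 |
| All kept, exits change by −0.5 | 0 |
| All kept, exits change by −1.0 | −0.014 to −0.018 |
| 5% leave per week, zero change | 0.5 × (1 − 0.95²) = 0.049 |
| 10% leave per week, zero change | 0.5 × (1 − 0.90²) = 0.095 |

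For the bias to reach 0.25 standard error with zero-change exits, the run-in exit share must be 0.25 × 0.171/0.5 = 8.6%, or 4.4 of 51.

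**The case against.** The strongest reply is that the phrase may simply mean study drug as allocated, run-in included. The Visit 2 description says run-in capsules were dispensed according to the allocated group, Table 1 counts run-in within total treatment duration, and the dosing text at one point treats run-in as part of the treatment period. The FAS also omits the word fixed from the defined term. This shows that the wording is ambiguous. It does not displace the literal reading, because the same documents repeatedly place run-in before the assigned dose and call it a lower dose.

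The restriction may also be deliberate: "The primary endpoint was change in HbA1c level post 12-week administration of selected fixed dose of USVCAP", and requiring one dose of that strength fits such an endpoint. That is a fair defence of the within-group tests. It does not justify applying the condition unequally in a comparison between groups, and no section states the intention.

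The point that the SAP may name another set stands in full and makes the concern conditional.

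A reader might infer that every early Group A leaver is kept. The documents do not support that: a post-baseline assessment is still required, and attendance at the withdrawal visit is not guaranteed. A reader might also infer that the rule favours the higher doses. That follows only if exits do worse than continuers. Withdrawal reasons include poor tolerability, uncontrolled hyperglycaemia and hypoglycaemia, which could act in opposite directions.

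**Conclusion.** The point holds in conditional form. As literally worded, FAS membership in Groups B and C depends on an open-label, investigator-judged event after randomisation, and in Group A it does not. If that set is used for the between-dose ANCOVA of HbA1c, fasting glucose or postprandial glucose, the comparison can be biased in a direction that the documents do not settle.

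Under even 20% dropout the HbA1c effect is small, as the figures above show. It would matter more if run-in exits approached one in twelve, and the documents give no count that rules this in or out. No size is given for the glucose endpoints because the documents state no SD for them.

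The documents do not support the stronger inference that the study's dose comparison, or its primary result, is invalid. The paired t-tests compare no groups; in B and C they would only be limited to subjects who reached the assigned dose. The per-protocol set requires completion in every group, so it has no such differential rule. This is worth correcting as a cheap improvement.

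**What to change.** Define the FAS as all randomised subjects who took at least one dose of any USVCAP strength, run-in doses included, and had at least one post-baseline assessment, analysed in the randomised group. Name it as the set for the between-dose ANCOVA. Keep the present definition as a supplementary set of subjects who reached the assigned dose. Add a table of run-in exits by group and reason; that table alone would show whether the issue has any practical weight.

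The study is written up as completed, so the re-analysis should be labelled post hoc, as the section on deviations from the statistical plan requires, unless the separate SAP already specifies this set. If it does, the FAS wording here should be aligned with it.

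The work is small and uses existing data. The cost is interpretive: HbA1c is scheduled only at screening and end of treatment, so run-in leavers would enter with a one- to two-week value or a carried-forward screening value. Neither measures 12-week response, and the Group B and C results may look slightly less favourable. Under the even-dropout, zero-change assumptions, Group C's mean reduction shrinks by 0.014 to 0.018 points, or 0.10 to 0.13 of its within-group standard error of 1/√51 = 0.140.
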